2.1.4 CDAD and AAD infection in care homes

There is limited data regarding antibiotic use, and incidence of AAD and CDAD in care homes. Most of the research to date has been carried out in hospital settings or in the US. However, residents in care homes in the UK have many of the risk factors associated with developing AAD and CDAD (e.g. over 65 years, frail, multiple co-morbidities).

Antibiotic use in US residential homes is common: estimations of single timepoint prevalence ranges from 8% to 17%. Between 50% to 75% of residents received at least one antibiotic prescription over a twelve-month period [8]. We conducted a prescribing audit of care homes in one Health Authority and found that 134 (7%) of 1901 residents were on an antibiotic on a single day. A study in care homes in Sweden showed 25% of service users were prescribed an antibiotic during a three month observation period.[12] Considerably fewer antibiotics are prescribed in Sweden compared to the UK.[13] We do not know how many of these service users developed AAD nor how many had *C. difficile*. Providing reasonable estimates of these outcomes for the UK relate to the scientific importance of our study to the NHS. Diarrhoea within long term care facilities can cause fatalities and may become endemic. Up to 33% of patients in secondary care in the UK develop diarrhoea after antibiotic treatment.

Laffan and colleagues retrospectively reviewed CDAD incidence and prevalence in a single 200 bed Long Term Care Facility (LTCF) in Baltimore in the US between July 2001 and December 2003. Incidence of CDAD ranged form 0 to 2.62 cases per 1000 resident days. They found that CDAD in this LTCF occurred most often in patients who had recently been admitted to hospital [14]. US studies by Kutty and colleagues and Chang and colleagues found that over 90% of post hospitalisation cases of CDAD occur within 30 days of discharge [15, 16] Riggs and colleagues in the US found that over 50% of patients admitted to a LTCF during an outbreak were asymptomatic carriers of *C.difficile* (stool culture positive but no diarrhoea) [17].

2.1.5 What are probiotics and why might they prevent AAD and CDAD?

Probiotics are dietary supplements containing a mono or mixed culture of live microorganisms such as bacteria or yeasts, which, when administered in adequate amounts, confer a health benefit on the host by improving the properties of the indigenous microflora [1]. Although the bacterial preparation to be used in this study is not yet known to confer a health benefit in this context, the term "probiotic" will be used for simplicity. Probiotics have been suggested as a treatment for antibiotic-associated diarrhoea, including *C. difficile*, as they reinforce the human intestinal barrier and help maintain the commensal gut flora [2, 18-20]. Probiotics are resistant to digestion by enteric or pancreatic enzymes, gastric acid and bile, and are thought to prevent the adherence, establishment and/or replication of pathogens in the gastrointestinal tract. Probiotics are generally well tolerated and free of adverse effects, although theoretically, the introduction of live bacteria may carry the risk of introducing antimicrobial resistance genes. In additional, there are a small number of case reports where probiotic organisms may themselves have caused infection.

A meta-analysis of 10 randomised, blinded placebo-controlled trials included 1862 pediatric and adult patients who received Lactobacillus as a single agent regimen or placebo to prevent AAD. The combined risk ratio of developing AAD was significantly lower with Lactobacillus compared with placebo (RR 0.35, 95% confidence interval [CI] 0.19-0.67). In a subgroup analysis, this held true for adults but not pediatric patients (RR 0.24, 95% CI 0.08-0.75 and RR 0.44, 95% CI 0.18-1.08, respectively)[21]

2.1.6 Conducting research in care homes

Conducting research studies in care homes, especially in nursing homes, poses unique challenges. Care home research participants are more likely to be older, more physically frail and more likely to be cognitively impaired compared to participants from other research settings [22]. Recruitment, consent, retention and data collection can be time consuming and difficult and extra time and help will need to be provided to ensure that the staff in care homes have the support to carry out the research procedures [23]. Junior care home staff turnover is frequent, though senior staff tends to remain in post long-term. Very little scientifically robust research has been conducted in care homes world wide including the UK. Good practice and excellent care require robust underpinning research and an important and increasing part of our population are resident in care homes.

2.2 Rationale for current Study

US and UK surveillance data (incomplete) and UK clinical experience suggests that AAD, including CDAD, could be an important problem in UK care homes. In addition, there are strong grounds for evaluating probiotics in conjunction with antibiotic treatment to prevent AAD in care home residents, but this has never been evaluated in a robust clinical trial. Before a trial is justified, the importance of the AAD problem to both the Independent Care Home sector and NHS, as well as a firm basis for sample size calculation and trial methodology need to be more clearly established (Stage 1).

To account for the anticipated difficulties, and to address unanticipated problems in conducting research in the care home setting, we plan to include sub studies within Stage 1 to inform and pilot procedures for the RCT in Stage 2. The substudies will test study procedures including giving the probiotic, model consent procedures, develop training materials for care home staff in how to conduct the RCT and determine if cascading of the training to new colleagues is possible. During Stage 1, the reliability of care home staff in identifying and recording aspects of diarrhoea episodes will also be established.

We will also conduct focus groups and qualitative interviews in order to broaden our understanding of consent in this vulnerable population.

3 Study objectives (Stage 1)

To establish the importance of the problem of AAD to service users, their families, care homes and the NHS, provide a firm basis for sample size calculation and ascertain the practicalities of conducting a randomised controlled trial in the care home setting.

3.1 Primary objectives

Observational study

1) To conduct prospective systematic ascertainment of the incidence of AAD in care homes;

2) To allow an appraisal of the estimated sample size for a Randomised Controlled Trial (RCT) in Stage 2;

3.2 Secondary objectives and sub-study objectives

Observational study

1) To conduct prospective systematic ascertainment of antibiotic use in care homes

2) To estimate the risk of AAD overall and from particular antibiotics in care home settings;

3) To identify barriers and implementation issues in conducting a trial of AAD prevention/amelioration in a care home setting.

Sub Study 1. Prevalence:

1) To determine the prevalence of asymptomatic *C. difficile* carriage in service users within selected care homes.

Sub Study 2 Qualitative Observational Study of Care Home Routines

- To better understand the range of daily care culture and schedules within care home settings (including delivery of food and drink, communication, skill mix, administration, visiting arrangements, toileting arrangements etc).
- To determine what level of assistance the care home staff require to deliver the study
- 3) To assess the level of data we can feasibly collect
- To assess the best method and timing of drug delivery and administration of probiotic/placebo
- 5) To determine whether study procedures are likely to be effectively communicated throughout the home.

Sub study 3. Qualitative:

 To conduct focus groups and individual qualitative interviews with service users, their family, care home staff and General Practitioners. To explore the ethical and practical issues of consent and assent, particularly the topic of advanced consent, for elderly residents who may/may not have capacity to consent

Sub study 4 - EQ-5D By Proxy

1) This sub- study is testing the hypothesis that there is an inverse relationship between agreement in subject/proxy EQ-5D scores and the

subject's level of cognitive competence. If results support this hypothesis, then a minimum level of cognitive competence will be identified below which EQ-5D data should be collected by proxy.

2) The study will also explore whether a combination of professional and friend/relative proxies would be preferable to either proxy alone.

4 Study design

Stage 1 of PAAD is a prospective observational study that will collect initial data (e.g. amount and type of antibiotics used, episodes of AAD and CDAD and outcome) for 12 months on 270 service users in a purposive sample of nine care homes in South Wales. This will identify the scale of the problem, provide incidence data to determine whether the trial (Stage 2) is justified, and if so, provide the basis of our sample size calculation. Certain research procedures for the RCT (Stage 2) will also be piloted and developed within Stage 1.

Within the first Stage there will be three sub studies imbedded within the main study (see section 17 for more details). These are:

1) Prevalence Sub Study:

To establish the asymptomatic carriage of *C. diff* in care home service users in each care home. This will occur during a one-week collection phase in each of the included care homes. This is an optional component for all service users.

Antibiotic prescribing data for the previous three months for each of the service users taking part in this sub study will also be collected. This will provide valuable research information for comparing to the antimicrobial sensitivities of bacterial isolates identified in baseline stool samples.

2) Sub Study 2 Qualitative Observational Study of Care Home Routines

PAAD sub-study 2 is a qualitative observation study which we aim to conduct in 5 of the 10 care homes participating in PAAD stage 1. Care home staff will be informed that a researcher is observing daily care routines. Service users and relatives will not be informed that a researcher is observing daily care routines.

Sub-study 2 is being conducted as a pre-research study (ie. to inform the design of PAAD stage 2) and not a research study.

3) Qualitative Sub Study:

To establish the feasibility and acceptability of taking advance consent/assent for research trial procedures in care home service users. This will be achieved through conduction of 18 focus groups with family members and care staff, and qualitative interviews with GPs and service users at nine homes.

4) EQ-5D by Proxy

This is an observational sub study involving up to 150 service users, their main carer and their most frequent visitor. Two of the larger Care Homes already recruited to the main PAAD study will be included in this sub-study so that the maximum number of SUs can be recruited from a minimum number of care homes. Consented SUs will be asked to complete the EQ-5D+C (a standard EQ-5D with one additional question for self-reported cognitive ability) with explanation from an independent researcher. If the SU is able to provide responses to the EQ-5D+C on this occasion, they will also be asked to complete the Mini-Mental State Examination (MMSE) by the researcher. The carer [and most frequent visitor, if available on-site] will be asked to complete two versions of the EQ-5D proxy questionnaire: (i) how the proxy would rate the SU's health (EQ-5D: 1) and (ii) how the proxy thinks the SU would rate his/her own health (EQ-5D: 2).

5 Recruitment of Care Homes

Care Homes located in South East Wales will be approached to take part in the PAAD Study. The Manager of the care homes will be approached to give permission for the care home to take part in the study and for all resident service users to be approached about the study. Each care home will need to have at least three interested staff to take responsibility for conducting the study in their care home. An agreement detailing roles and responsibilities will be signed by the care home manager and Cardiff University. Discussions will be held regarding resources required and implications regarding an increase in *C. difficile* findings.

Care homes will be split into three strata, based on the type of care home: nursing, residential and dual. After care homes in each stratum are identified, corresponding care home managers will be approached at random until three care home managers in each stratum have given permission for their care home to participate in the study. Nine care homes will be recruited in total.

Before any care home can begin recruitment the PAAD Trial Manager will provide the care home with the essential documents to conduct the study. The senior care home staff / nursing staff will ensure that the following documents have been received by the PAAD Trial Manager:

- The approval letter from the Centre's R&D Department, following submission of the Site Specific Information (SSI) form (if required);
- > A signed Study Agreement (care home lead and sponsor signature);
- Completed contacts list of all site personnel working on the Study (see appendix 2);
- Completed Signature List and Roles and Responsibilities document (see appendix 3);
- Consent forms and Patient Information Sheet (PIS) on centre letter headed paper;

In addition to the study specific documents SEWTU will also provide the care home with:

- > C. difficile Information leaflet;
- > A DH Infection Control guidance document for care homes, regarding management of symptomatic service users identified with *C. difficile*.

Upon receipt of all the above documents, the PAAD Trial manager will send a confirmation letter to the care home lead detailing that the centre is now ready to recruit patients into the study. This letter will be filed in each of the care homes Site File. Along with this confirmation letter, any additional documents required to recruit a patient into the PAAD Study will be included.

6 Participant selection

Patients are eligible for the trial if they meet all of the following inclusion criteria and none of the exclusion criteria. All queries about patient eligibility must be directed to the PAAD Trial Manager in the first instance before recruitment.

6.1 Inclusion criteria

1) Service users who are/have been admitted to the care home for >24 hours;

2) Planned admission to care home of one month or more (excludes short term respite care);

3) Provided written confirmed consent/assent provided.

6.2 Exclusion criteria

There are no exclusion criteria for the PAAD Observational Study.

7 Recruitment

7.1 Number of participants

A total of 270 participants will be required for the main observational study of Stage 1.

Due to the age group of the participants and the multiple co-mordities associated with this age group of participants, it is likely that the total number of participants recruited may be reduced during the specified recruitment period. This is expected due to participants who may pass away or withdrew their consent/assent to remain in the study. Any loss in the target number of recruited participants will be compensated by continuing the recruitment period to three months prior to the end of the study. This may result in maintenance of the total number of participants or greater than this target figure.

7.2 Recruitment and consent of service users into main observational study and the prevalence sub study

We will aim to recruit all eligible service users from each care home at the outset and obtain consent or assent to follow them for one year within the main observational study.

There are likely to be two types of service users who are eligible to join the study; those who are have capacity and are able to consent for themselves and those unable to consent for themselves (lack capacity), whereby consent procedures will differ. Either trained senior care home staff / nursing staff or

trained PAAD study research nurses will be responsible for consenting service users.

The following basic steps will be implemented within care homes with local adaption documented.

- 1. Senior care home staff / nursing staff will identify those service users who are eligible to join the study.
- 2. Senior care home staff / nursing staff will identify representatives for each service user (i.e. next of kin, those who visit most regularly etc).
- 3. Senior care home staff / nursing staff or the PAAD research nurses taking consent will assess mental capacity by periodically checking, during the consent procedure, that the information the service user has been given (either the full information sheet or pictorial information sheet, in large print, or verbal explanation) is fully understood by the service user.
- 4. Where service users have capacity, the service user will sign and date the consent form, with the trained senior care home staff / nursing staff or research nurse taking consent. If the service user consents and agrees, then the service user's representative will be informed that the service user is taking part in the study, and will be sent information about the study.
- 5. Where service users lack capacity, the service user's representative (consultee) will be provided with information about the study and will be asked for advice about whether or not the service user would want to join the study. The representative will be asked to provide assent for the service user to join the study.
- If no next of kin or representative can be contacted we will, as suggested by the 2005 Mental Capacity Act s32(3), nominate an appropriate person, e.g. Age Concern Advocate or GP, to give advice. (http://www.opsi.gov.uk/acts/acts2005/20050009.htm).

The following information sheets will be provided to the care homes:

Service user

- 1) Summary service user information sheet
- 2) Pictorial service user information sheet
- 3) Detailed service user information sheet
- 4) Service user consent form

Service user's representative

PAAD Study: Establishing the platform. Version 7.0 , dated 17/08/2011 23

- 1) Detailed consultee information sheet
- 2) Consultee consent form

We will repeat this process for any new permanent resident moving into participating care homes up to five months following recruitment start in that care home.

The service user / representative must personally sign and date the latest approved version of the informed consent form before any study specific procedures are performed.

The service user / representative will be allowed as much time as wished, to consider the information, and the opportunity to question the care home staff, study research nurse, their GP or other independent parties to decide whether they will participate in the study. Written Informed Consent/Assent will then be obtained by means of participant dated signature and dated signature of the person who presented and obtained the informed consent/assent. The person who obtained the consent/assent must be suitably qualified and experienced, and have been authorised to do so by the Chief Investigator. A copy of the signed Informed Consent/assent will be given to the participants/consultee. The original signed form will be retained at the study site. All consultees who have not responded will be contacted by phone at least once by the care home staff.

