8.2.1 End of Study Search of Medication Records

At the end of the recruitment period the antibiotics prescribed for each consented service user, as determined from the PAAD Case Record Forms (CRFs), will be checked against the original Medication Records retained with the Care Home Plan for each service user. This data will be collected by Trial Manager, Trial Data Manager, Research Nurses and NISCHR Research Officers. A separate CRF will be designed to transcribe this data.

This procedure will be carried out to determine whether all antibiotics prescribed for service users, recruited at care homes, has been captured as part of the PAAD Observation study.

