While disagreement between responses by any subject and his/her proxies can clearly be due to factors other than cognitive impairment, it is still anticipated that on average, the level of agreement in each of the above analyses will get closer to the level of agreement for a 'clearly cognitively competent' sub-group alone. These results will allow exploration of the MMSE score below which EQ-5D data should be collected by proxy in the RCT.

13 Study closure

Trial centres will be notified not to collect any further data post the participant closest to the 12 month data collection period month. The study end date is deemed to be the date of last data capture.

14 Regulatory issues

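### The end-of-study antibiotic check is timed to the close of recruitment, for which the protocol gives two dates

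*Protocol*

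**What the plan says.** **The check.** Protocol 8.2.1 carries the heading "End of Study Search of Medication Records". Its first sentence sets the timing: "At the end of the recruitment period the antibiotics prescribed for each consented service user" are compared with the original medication records kept in the care home. Its last paragraph gives the aim: "This procedure will be carried out to determine whether all antibiotics prescribed for service users" at participating homes had been captured by the study.

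**The close of recruitment.** Section 7.1 expects deaths and withdrawals and says that the shortfall "will be compensated by continuing the recruitment period to three months prior to the end of the study", so that the total is held at 270 or exceeded. Section 7.2 intends to approach every eligible resident at the outset and to "obtain consent or assent to follow them for one year within the main observational study". It then repeats the consent process for "any new permanent resident moving into participating care homes up to five months following recruitment start in that care home". Neither section refers to the other.

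**The end of the study.** Section 13 tells centres "not to collect any further data post the participant closest to the 12 month data collection period month" and equates the study end with the last data capture.

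**The sample size.** Section 11.1 takes about 270 residents, 40% of them prescribed an antibiotic over 12 months, and states a 95% confidence interval of ±10 points around an AAD rate of 25%.

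**The concern.** The check in 8.2.1 is the protocol's safeguard against missed antibiotic courses. A check that runs when recruitment closes cannot see courses prescribed afterwards, so its timing works against its aim. Because recruitment has two closing dates, staff also cannot tell when the check falls due.

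The routine copying of medication records in 8.2 does not fill the gap. After baseline, a copy is made when a course is already known to the study, so a resident whose only course was missed triggers none. Unrecorded courses lower the ascertained antibiotic use, which is the first secondary objective in 3.2.

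The two closing dates collide on the group that 7.1 depends on. If all eligible residents are approached at the start, replacements must come largely from new arrivals, and 7.2 stops consenting those at five months. Separately, 7.1 treats replacement as a head count, although the 40% behind the sample size belongs to a full year of observation.

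**Working it through.** **1. Share of follow-up after the check.** Inputs: 12 months of data collection (sections 4 and 13); recruitment closing 3 months before the end (7.1) or 5 months after a home's recruitment start (7.2). Assumptions: the study ends 12 calendar months after the home starts, and the body of 8.2.1 is followed.

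- 7.1 rule: close at month 12 − 3 = 9, leaving 3/12 = 25% unreconciled.
- 7.2 rule: close at month 5, leaving (12 − 5)/12 = 7/12 = 58% unreconciled.
- The two dates are 9 − 5 = 4 months apart.

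If instead each resident is followed for a personal year, a check at month 5 still leaves 7 of 12 months for someone enrolled on day one, and all 12 for someone enrolled at month 5. That reading does not shrink the gap under the 7.2 rule.

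**2. What a late entrant contributes.** Assumption: constant prescribing hazard, calibrated to 40% in 12 months. Then P(antibiotic within m months) = 1 − 0.6^(m/12).

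| Months observed | P(antibiotic) | Relative to 40% |
|---|---|---|
| 3 | 12.0% | 0.30 |
| 7 | 25.8% | 0.64 |
| 12 | 40.0% | 1.00 |

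Ten replacements observed for 3 months would be expected to yield 10 × 0.12 = 1.2 treated residents, against 10 × 0.40 = 4 for a full year. AAD is counted for up to 8 weeks after stopping treatment (Definitions), so only about the first month of a 3-month stay allows a complete AAD window.

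**3. Whether the planned precision is at risk.** Treated residents: 270 × 0.40 = 108. The simple binomial half-width is 1.96 × √(0.25 × 0.75/108) = 8.2 points. The stated ±10 is therefore wider than its inputs give, that is, conservative. A half-width of 10 needs 1.96² × 0.1875/0.10² = 72.03, so 73 treated residents. The tolerable loss with no replacement is 1 − 72.03/108 = 33%.

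The protocol gives no loss rate, so a range follows. Lost residents are counted as contributing nothing (worst case), and replacement is one for one.

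| Loss | Half-width, no replacement | Half-width, 3-month replacements |
|---|---|---|
| 10% | 8.6 | 8.5 |
| 20% | 9.1 | 8.8 |
| 30% | 9.8 | 9.2 |
| 40% | 10.5 | 9.6 |
| 50% | 11.5 | 10.1 |

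With 3-month replacements, ±10 is first missed at about 48% loss.

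Clustering by home is the one route by which this slack could vanish. A design effect of (10/8.17)² = 1.50 would use all of it. With 108/9 = 12 treated residents per home, assumed intraclass correlations of 0.02, 0.05 and 0.10 give half-widths of 9.0, 10.2 and 11.8 before any loss. The protocol states no such value.

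**The case against.** **Heading and aim both point to a whole-study check.** A reader might infer from the body of 8.2.1 that months of prescriptions will certainly go unchecked. The documents do not support that: one phrase conflicts with the section's own heading and purpose, and the 58% further needs the 7.2 date to prevail over 7.1. This stands, so the finding is a contradiction with a conditional consequence. It still needs repair, because the body is the instruction that staff would act on.

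**The two dates can be read together.** Section 7.1 speaks of continuing a recruitment period to make good losses, which fits an extension beyond a routine five-month window. That is a fair reading, but the protocol does not say so.

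**Late recruits and precision.** A reader might infer that late replacements cannot restore the planned ±10. The protocol's own figures refute this: 108 treated residents are planned and 73 suffice. Section 7.1 also allows recruitment above target, so one-for-one replacement is only an assumption. What remains is that the word used in 7.1 for replacement promises more than late entrants deliver.

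**Bias in the AAD rate.** A reader might also infer that missed courses bias the AAD rate. That would need missed courses to carry a different AAD risk, or to be counted as AAD-free, and the protocol says neither. A missed course has no stool chart, so a later check would reveal the course but not its AAD outcome.

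**Conclusion.** The point holds in a limited form. Section 8.2.1 contradicts itself on when the antibiotic check is done, and the date it names is fixed in two unreconciled ways. On a 12-calendar-month study with the body text followed, 25% to 58% of the observation period falls after the check. Any course missed there lowers the prescribing rate. The number of such courses cannot be estimated from the protocol.

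It also holds that late recruits do not replace lost exposure one for one: about 0.30 of a full-year participant at 3 months, given a constant hazard. This does not put the ±10 precision out of reach under simple binomial sampling, and no effect on the AAD rate has been shown. How courses found only at the check are classified, and whether resident-months are tracked, are matters for the analysis plan or preferences in monitoring and form no part of the finding.

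**What to change.** - **8.2.1:** move the timing in the first sentence from the close of recruitment to the end of data collection, so that it agrees with the heading and the aim.
- **7.1 and 7.2:** state one recruitment closing rule, or say that 7.1 is a conditional extension of the five-month window in 7.2.
- **7.1:** replace the statement that extended recruitment compensates for losses by one saying that it maintains the number enrolled, and that late entrants contribute less observation time and fewer antibiotic courses.

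The cost is small. These are wording changes, and the same record check is done once, later, over more months of records.
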